10. Rubin DB. Comment: Neyman (1923) and Causal Inference in Experiments and Observational Studies. *Stat Sci*. 1990;5(4):472-480.
12. R Core Team. *R: A Language and Environment for Statistical Computing*. R Foundation for Statistical Computing; 2022. <http://www.R-project.org>

Sustainable East Africa Research in Community Health (SEARCH) Collaboration

Statistical Analysis Plan for Dynamic HIV Choice Prevention at Antenatal Clinics in Phase A of SEARCH-Sapphire

[name], PhD¹
and the SEARCH Study Team²

July 11, 2022

v1.0

¹University of California, Berkeley

²www.searchendaids.com

Table of Contents:

1. Study Overview	2
2. Population and Characteristics	3
3. Endpoint Measurement and Definition	3
4. Evaluation of the SEARCH DCP Intervention Effect	4
5. Intervention Implementation	5
Appendix: Power calculations	6
References	7

1. Study Overview

In Phase A of SEARCH-Sapphire (NCT04810650), we are conducting an individually randomized controlled trial to evaluate the effect of Dynamic Choice HIV Prevention (DCP) delivered to women recruited from antenatal clinics (ANC) on biomedical HIV prevention coverage in rural Kenya and Uganda. Details of the trial design and procedures can be found in the corresponding Study Protocol. Analyses plans for qualitative outcomes and cost-effectiveness outcomes are available elsewhere. Power calculations are given in the Appendix.

In brief, from April-July 2021, we enrolled 400 participants who were currently or anticipated being at risk of HIV. These participants were randomized to the DCP intervention or the standard-of-care using a stratified random block design. The stratification factors were country and pregnancy status, and the random block sizes were 2 and 4. The randomization list was generated by an independent researcher.

The DCP intervention includes choice of HIV prevention product (oral pre-exposure prophylaxis [PrEP] or post-exposure prophylaxis [PEP]), choice in HIV testing, choice in service location, and provider training on patient-centered care. Follow-up is over 48 weeks.

The primary objective is to evaluate if the DCP intervention improved biomedical HIV prevention coverage, defined as the proportion of the follow-up where the participant self-reported using PrEP or PEP. Secondary endpoints include biomedical covered time during periods of self-assessed HIV risk (compared between randomized arms) as well as coverage and uptake of the DCP intervention components (within intervention arm only).

2. Population and Characteristics

The population of interest is persons aged 15+ years who are seen at ANC and report current or anticipated HIV risk, as assessed via the country-specific Ministry of Health screening tools or self-assessment.

To characterize measurement of this population, we will provide a participant flow diagram (i.e., a CONSORT diagram). Overall and stratified by trial arm, we will summarize the baseline characteristics, including age, country, marital status, occupation, HIV risk criteria, alcohol use (any in prior 3 months), mobility (nights away in the past 3 months), pregnancy, and any prior use of PrEP or PEP in the past 6 months. We will categorize age in “younger” if aged 15-24 years.

3. Endpoint Measurement and Definition

At week-24 and week-48 of follow-up, surveys will be administered to assess HIV risk, possession of PrEP pills, possession of PEP pills, use of PrEP (any doses taken), and use of PEP (any doses taken). The assessment is by month and covers the prior 6 months. We will visualize these data with heatmaps and describe changes in product use over time and by self-reported risk.

The **primary endpoint of biomedical HIV prevention coverage** (a.k.a., biomedical covered time) is the proportion of follow-up where the participant reports taking PrEP or PEP. Thereby, this endpoint has a minimum of 0% (no use) and a maximum of 100% (full coverage). Persons contribute follow-up time when they respond to a survey. Persons who fail to complete both week-24 and week-48 surveys are missing in the primary analysis. Persons with incident HIV infection are assumed not to be covered during the period prior to seroconversion.

Using these data, we will also define the following **secondary endpoints**:

- Biomedical covered time at-risk, where follow-up is restricted to months of self-reported risk
- Possession covered time, defined as the proportion of follow-up where the participant reports having or receiving PrEP or PEP pills
- Possession covered time at-risk
- Use/possession ratio, defined as the proportion of follow-up with PrEP or PEP pills where the participant reports taking them
- Use/possession ratio when at-risk

4. Evaluation of the SEARCH DCP Intervention Effect

We will assess the Dynamic Choice Prevention intervention effect with targeted minimum loss-based estimation (TMLE), which improves precision and power by adaptively adjusting for baseline outcome predictors.^{1–5} Here, we will use **TMLE with Adaptive Pre-specification** to flexibly control for baseline covariates, while maintaining Type-I error control and accounting for the randomization scheme.^{6–8} Using 10-fold cross-validation, we will chose the optimal approach for estimating the outcome regression (i.e., the expected outcome given the randomization arm and adjustment covariates) and the known propensity score (i.e., the conditional probability of being randomized to the intervention given the adjustment covariates). Specifically, we will select the combination of estimators (adjustment variables + approach) that minimizes the cross-validated variance estimate.

Our pre-specified, candidate adjustment variables consist of pregnancy status at enrollment, age, country, use of PrEP/PEP in the 6 months before enrollment, and nothing (i.e., unadjusted). Our pre-specified, candidate learners consist of generalized linear models (GLMs) adjusting for a single variable (beyond the intervention indicator), stepwise regression, multivariate adaptive regression splines (MARS), and the arm-specific mean outcome.

Primary effect estimates will be for the study sample and on the **difference scale**: $1/n \sum_{i=1}^n [Y_i(1) - Y_i(0)]$, where $Y_i(1)$ denotes the counterfactual outcome for participant i under the intervention and $Y_i(0)$ denotes the counterfactual outcome for participant i under the control.^{9–11} Secondary comparisons will be on the ratio scale.

We will test the **null hypothesis** that the intervention did not change biomedical covered time with a two-sided test at the 5% significance level. We will also report point estimates and 95% confidence intervals for each effect measure and the arm-specific outcomes. Standard error estimation will be based on the estimated influence curve, and statistical inference will follow from the Central Limit Theorem (i.e., using the standard normal distribution).¹

Secondary analyses: To assess the robustness of these findings, we will repeat these analyses using the unadjusted effect estimator. We will also repeat these analyses using TMLE to adjust for missing endpoints.

Subgroup analyses: We will repeat these analyses within strata defined by country, pregnancy status at enrollment, age group, alcohol use, and use of PrEP/PEP in the 6 months before enrollment. In subgroups with fewer than 41 participants, we will limit the

candidate estimation approaches to main terms adjustment for a single covariate or the simple mean and use leave-one-out cross-validation. To further understand effect heterogeneity, we may conduct variable importance measures (i.e., unadjusted and adjusted predictor analyses) with TMLE.

Secondary endpoints compared by arm: We will implement analogous analyses to evaluate the intervention effect on biomedical covered time at-risk, possession covered time (overall and at-risk), and use/possession ratio (overall and at-risk).

Validation of self-report: Since the primary and key secondary study endpoints rely on self-report, we will objectively measure adherence using drug levels in small hair samples collected among participants reporting any PrEP or PEP doses taken in the past 30 days. Overall and by arm, we will report the number and proportion of these participants with detectable tenofovir levels (>0.002 ng/mg) in their hair at week-24. Using a two-sample test, we will formally test the null hypothesis of equal proportions between arms. We may repeat these analyses at week-48.

Additional descriptive analyses: Overall and by arm, we will report the number and proportion of participants who withdrew, died, or seroconverted. We will provide seroconversion narratives and may test the null hypothesis of the HIV incidence rate is the same between arms through Poisson regression with person-years-at-risk as offset.

5. Intervention Implementation

Within the intervention arm, we will describe coverage and uptake of the DCP intervention at baseline (week-0), week-4, week-12, week-24, and week-36:

- Visit coverage: number and proportion who attended study visits
- Choice of prevention product: number and proportion who selected PrEP, PEP, condoms, or nothing
- Choice of HIV testing: number and proportion who selected a self-test or rapid HIV test
- Choice of service location: number and proportion who selected to have visits at clinic or at an out-of-facility location (e.g., home)

All metrics will exclude persons who died, withdrew, or seroconverted by that week of follow-up.

[figure not shown]
We will also characterize ever use of DCP intervention components over follow-up. We may also report on reasons for product changes, barriers to care, plans to address

those barriers, and utilization of the phone hotline. We will report these metrics overall and within key subgroups.

10. Rubin DB. Comment: Neyman (1923) and Causal Inference in Experiments and Observational Studies. *Stat Sci*. 1990;5(4):472-480.
12. R Core Team. *R: A Language and Environment for Statistical Computing*. R Foundation for Statistical Computing; 2022. <http://www.R-project.org>

A Multisectoral Strategy to Address Persistent Drivers
of the HIV Epidemic in East Africa (SAPPHIRE)

Sustainable East Africa Research in Community Health (SEARCH) Consortium

Statistical Analysis Plan

**Project: Effect of Community Health Worker Facilitated Telehealth
Intervention for Severe Hypertension Management in SEARCH
SAPPHIRE**

[name]*
[name], MPH, PhD**
[name]***
[name], PhD*
[name], MMed, MPH, PhD****
[name]***

for the SEARCH Collaboration

June 1, 2023

Version 1.0

*School of Public Health, University of California Berkeley, Berkeley, USA

**Kenya Medical Research Institute, Nairobi, Kenya

***Division of HIV, ID, & Global Medicine, Department of Medicine, UCSF, San Francisco, USA

**** Makerere University, Department of Medicine, Kampala, Uganda

Table of Contents

1. Overview.....	2
2.1 General approach for evaluating intervention effects.....	3
2.2 Evaluate the effect on hypertension control at week 24 and 48	4
2.3 Evaluate the effect on retention in care at week 24 and 48.....	5
2.4 Evaluate the effect on average systolic blood pressure at week 24 and 48	5
2.5 Evaluate the effect on time to hypertension control	5
2.6 Assess predictors of hypertension control and retention in care.....	5
Appendix: Power calculations	6
References	7

1. Overview

The SEARCH-Sapphire Severe Hypertension (HTN) Treatment study is an individual randomized controlled trial testing the hypothesis that community-based hypertension care (intervention) will improve control of hypertension, as compared to clinic-based, patient-centered care (control) in adults aged 40+ with severe hypertension (blood pressure $\geq 160/100$ mmHg). The community-based intervention consists of clinician telehealth combined with lay health worker blood pressure measurement and medication delivery. The pilot trial takes place in three communities in Kenya and Uganda and began enrollment in May 2022.

After community-based screening by community health workers, individuals with severe hypertension were referred to the nearest government-run clinic for clinical assessment and enrollment. Following enrollment and completion of an initial clinic visit, participants were randomized to the intervention (n=98) or control (n=102) conditions. To ensure balance between arms, randomization was stratified by country and sex and was implemented by an independent statistician using a stratified random block design with random block sizes 2 and 4.

Intervention participants received home-based, follow-up care for hypertension, which consisted of blood pressure measurement and adherence assessment using pill count by a community health worker, a telehealth visit with a clinician, and medication dispensation by the community health worker according to clinician orders. Control participants received clinic-based integrated, patient-centered hypertension care, detailed elsewhere.¹⁻³ Treatment guidelines for use of antihypertensive medication for both study arms were based on standard country guidelines. Additional details of the study procedures are available in the Study Protocol.

The primary objective of this study is to determine whether the intervention improved hypertension control at 24 weeks. Secondary endpoints include retention in care, mean systolic blood pressure at 24 and 48 weeks, and hypertension control at 48 weeks. We will also characterize changes in hypertension severity and evaluate predictors HTN control and retention.

Throughout, the population of interest comprises non-pregnant adults, aged 40+ if blood pressure was elevated at both community-based and clinic measurement (≥ 140 mmHg systolic or ≥ 90 mmHg diastolic) and moderate-severely elevated on at least one of these measurements (≥ 160 mmHg systolic or ≥ 100 mmHg diastolic). Participants were excluded if they were pregnant – these individuals were immediately referred to the prenatal clinic for evaluation and treatment of hypertension in pregnancy.

We will provide descriptions of participant flow through the study (i.e., a consort diagram), measurement coverage, and baseline characteristics (e.g., country, age, sex, prior history of hypertension diagnosis and baseline treatment, comorbidities, and baseline severity of hypertension). We will also report risk factors (N and %) for uncontrolled hypertension at enrollment. We will provide these descriptive statistics, overall and by arm.

2.1 General approach for evaluating intervention effects

We will assess the intervention effect with targeted minimum loss-based estimation (TMLE), which provides precision and power gains over an unadjusted effect estimator (e.g., a t-test) by adjusting for baseline predictors of the outcome.⁴⁻⁷ For a detailed review of TMLE and its relation to other effect estimators in randomized trials, we refer the reader to Colantuoni and Rosenblum.⁸ For a recent demonstration of the improved precision offered by TMLE in randomized trials, we refer the reader to Balzer et al. and to Benkser et al.^{9,10}

Here, we will use **TMLE with Adaptive Pre-specification**, a fully automated procedure to flexibly adjust for baseline outcome predictors, while maintaining Type-I error control.^{11,12} Specifically, using 10-fold cross-validation, we will chose the optimal approach for estimating the expected outcome given the trial arm and baseline covariates (a.k.a., the outcome regression) and for estimating the conditional probability of being randomized to the intervention given the baseline covariates (a.k.a., the propensity score). Throughout, optimality is defined by using the squared (estimated) influence curve for the TMLE as loss function. Thereby, we will select the combination of estimators (adjustment variables + approach) for the outcome regression and the propensity score that minimizes the cross-validated risk estimate and, thus, maximizes empirical efficiency.

Our pre-specified, candidate adjustment variables are age, sex, baseline HTN severity as assessed at enrollment (“grade 1” as 140-159/90-99 mmHg; “grade 2” as 160-179/100-109 mmHg, and “grade 3” as $\geq 180/110$ mmHg), country, and nothing (i.e., unadjusted). Our pre-specified candidate estimators are main terms, stepwise

regression, adjustment for a single covariate, and the mean. In sensitivity analyses, we will also implement that unadjusted effect estimator as the contrasts of average outcomes by arm.

Primary estimates will be for the study sample and on the **difference scale**:

$\frac{1}{n} \sum_{i=1}^n [Y_i(1) - Y_i(0)]$, where $Y_i(1)$ denotes the counterfactual outcome for participant i under the intervention and $Y_i(0)$ denotes the counterfactual outcome for participant i under the control. Secondary comparisons will be on the relative scale.

For all endpoints, we will test the **null hypothesis** of no change in outcomes due to the intervention with a two-sided test at the 5% significance level. We will also report point estimates and 95% confidence intervals for each effect measure and the arm-specific average outcomes. Standard error estimation will be with the estimated influence curve, and statistical inference will follow from the Central Limit Theorem (i.e., using the standard normal distribution).⁴

For all endpoints, we will also examine the intervention effect within subgroups defined by sex, age group (<60 years vs. ≥ 60 years), country, baseline HTN severity, and HIV status. In subgroups with fewer than 51 participants, we will conduct unadjusted analyses.

2.2 Evaluate the effect on hypertension control at week 24 and 48

The primary endpoint is hypertension control at week 24, evaluated in all participants in a research visit at week 24 and defined as blood pressure $< 140/90$ mmHg on the average of the second and third measurements. Participants who miss their week 24 visit and, thus, are missing blood pressure measurement at week 24 will be assumed to be uncontrolled.

As described above, we will use TMLE with Adaptive Pre-specification to compare hypertension control between intervention and control arms and to test the null hypothesis that the intervention did not impact hypertension control. We will conduct sensitivity analyses using TMLE to adjust for differences in characteristics (e.g., arm, age sex, sex, country, baseline severity) between persons with measurements and persons with missing measurements. We may conduct an additional sensitivity analysis excluding participants with missing values.

A secondary endpoint is hypertension control at week 48, assessed in the same manner as hypertension control at week 24.

At week 24 and week 48, we will also evaluate the intervention impact on hypertension severity, defined as participants with grade 2 or higher hypertension. For the severity endpoint, our primary approach will be TMLE to adjust for differences between persons with and without measured outcomes, and the secondary analysis will exclude participants with missing outcomes.

2.3 Evaluate the effect on retention in care at week 24 and 48

Using an analogous approach, we will formally compare retention in care by trial arm at week 24 and at week 48. We define retention in care as not late for the most recent scheduled hypertension care appointment by 30 days or more. This endpoint is not subject to missingness. Within TMLE and Adaptive Pre-specification, we will use the same candidate adjustment variables and approaches as the primary endpoint. Sensitivity analyses will be unadjusted.

2.4 Evaluate the effect on average systolic blood pressure at week 24 and 48

We will assess the intervention effect on mean systolic blood pressure at week 24 and week 48. Mean systolic blood pressure will be assessed using the average of the second and third blood pressure measurement taken by research staff at these timepoints. We will use the same candidate adjustment variables and estimation approaches as the primary endpoint.

In the primary approach, we will assume persons without a blood pressure measurement at the timepoint of interest are out-of-care and their blood pressure has reverted back to baseline. In other words, we will impute missing systolic blood pressure measures with their baseline measure. In sensitivity analyses, we will control for incomplete ascertainment of blood pressure measures. Specifically, we will use TMLE to adjust for differences in characteristics between persons with measurements and persons without measurements. For comparison, we may also conduct a complete-case analysis (i.e., restricting to participants with known outcomes.)

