Dynamic Treatment	Mobile Travel Pack intervention 1. Age ≥ 15 years 2. HIV-positive 3. HIV RNA non-suppression (>400 c/mL in the prior 12 months) or missed 2 visits in past 12 months or no VL measured in past 12 months 4. Travel outside the community ≥ 2 times in past 12 months 5. Enrolled or new to care in a study clinic Alcohol intervention 1. Age ≥ 18 years 2. HIV-positive 3. HIV RNA non-suppression (>400 c/mL in the prior 12 months) or missed clinic visits (>2 weeks or ≤ 90 days from last scheduled clinic visit) within past 6 months, or out of care without return to care (>90 days from last scheduled clinic visit) within past 6 months 4. Heavy alcohol use per AUDIT-C tool (scores of ≥ 4 for men, and ≥ 3 for women) 5. Enrolled or new to care in a study clinic Hypertension Linkage and Treatment Interventions	Mobile Travel Pack intervention 1. <15 years of age 2. Participation in another Phase A RCT intervention component Alcohol intervention 1. <18 years of age 2. Participation in another Phase A RCT intervention component 3. No access to mobile phone Hypertension Linkage and Treatment Interventions

	
 1. Age ≥ 25 years (linkage); age ≥ 40 years (treatment) 2. Blood pressure $\geq 140/90$ mmHg on three repeated measurements during community-based hypertension screening for linkage study and $\geq 160/100$ mmHg for the treatment study 3. Resident (by self-report) within catchment area of referral health center 	
 1. <25 years (linkage); age <40 years (treatment) 2. Plan to out-migrate from the catchment area of referral health center within 30 days of screening visit 3. Already engaged in hypertensive care (by self-report) (linkage only) 4. Blood pressure measure of $\geq 180/110$ mmHg during screening and symptoms of hypertensive emergency (linkage only) 5. Pregnant (treatment) 6. Co-morbidities that preclude home monitoring (treatment)
--	--	--

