The SEARCH SAPPHIRE Hypertension Linkage study is an individual randomized controlled trial, designed to test the hypothesis that a transportation voucher and a follow-up phone call will improve linkage to clinic-based hypertension care following community-based screening. The trial takes place in three communities in Kenya and Uganda and began enrollment in June 2021. After community-based screening, individuals diagnosed with hypertension (HTN) were enrolled and given a clinic appointment at the nearest government-run clinic. Participants randomized to intervention (n=100) received a voucher to reimburse transport expenses, redeemable upon clinic linkage at any time following enrollment (even if initial linkage appointment was missed). Intervention participants who missed their initial linkage appointment also received a follow-up phone call to encourage linkage. Control participants (n=100) did not receive a transport voucher or any follow-up if they missed their initial linkage appointment. Upon linkage to care, all participants received integrated, patient-centered hypertension care, detailed elsewhere.¹⁻³ Treatment guidelines for use of antihypertensive medication were based on standard country guidelines. Additional details of the study procedures are available in the Study Protocol.

The primary objective of this study is to determine whether the intervention improved linkage to HTN care by 30 days. Secondary endpoints include linkage at or before the scheduled appointment, linkage by 3 months, HTN control at follow-up, and retention in hypertension care. We will also characterize changes in HTN severity and evaluate predictors of linkage, HTN control, and retention.

Throughout, the population of interest comprises non-pregnant adults, aged 25 years and older, who do not have a prior diagnosis of hypertension, and who have uncontrolled HTN at baseline as identified through community-based screening (defined as systolic blood pressure ≥ 140 mmHg or diastolic blood pressure ≥ 90 mmHg on all three baseline measures). Participants were excluded if they had a blood pressure $\geq 180/110$ mmHg and had symptoms of hypertensive emergency – these individuals were immediately transported to the nearest health facility for emergent treatment.

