intervention impact on HTN severity, defined as participants with grade 2 or higher HTN at follow-up, and on the average of the second and third systolic blood pressure measures at follow-up.

2.5 Evaluate the effect on retention in hypertension care at 3, 6 and 12 months

We will define retention in care as not late for the most recent scheduled hypertension care appointment by 30 days or more. This endpoint is also not subject to missingness. Again, we will use the primary analytic approach of TMLE with Adaptive Pre-specification to assess the intervention effect on retention in hypertension care at 3, 6 and 12 months and to test the null hypothesis that the intervention did not improve retention in care at 3, 6 or 12 months, respectively. For this endpoint, the candidate adjustment variables will be expanded to include baseline HIV status. We will implement analogous subgroup analyses.

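### The severe-hypertension SAP leaves prior diagnosis and baseline antihypertensive treatment off the candidate adjustment list, so the primary analysis cannot use them even if they are prognostic

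*SAP*

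**What the plan says.** All SAP references are to the severe-hypertension treatment SAP unless another is named.

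- **Candidate list (2.1).** "Our pre-specified, candidate adjustment variables are age, sex, baseline HTN severity as assessed at enrollment". Severity has three grades. Country and no adjustment are the only other entries. The procedure selects the combination of variables and estimators with the lowest cross-validated risk.
- **Data available (1. Overview).** The baseline description, overall and by arm, includes "prior history of hypertension diagnosis and baseline treatment, comorbidities, and baseline severity of hypertension".
- **Who can enter (Protocol 7.3.1).** Being in care already is an exclusion for the other hypertension trial only: "Already engaged in hypertensive care (by self-report) (linkage only".
- **Randomization (1. Overview).** "randomization was stratified by country and sex", and "participants were randomized to the intervention (n=98) or control (n=102) conditions".
- **Test (2.1).** The null hypothesis is "no change in outcomes due to the intervention with a two-sided test at the 5% significance level".
- **Purpose of adjustment (Protocol 15.2).** TMLE is meant to gain precision by adjusting for the stratification factors and for chance imbalance on further baseline predictors of the outcome.

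**The concern.** The sample can mix people on no drugs with people whose pressure is high despite drugs. The candidate list codes both by grade alone. It is a reasonable argument that the same grade means something different in the two groups, although the SAP does not make it. If treatment status predicts week-24 control beyond age, sex, grade and country, the primary TMLE cannot use that information, because the variable is not on the list.

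The programme's other SAPs usually include a counterpart. The mobility and alcohol SAPs list baseline viral suppression, and the three prevention SAPs list earlier PrEP/PEP use. In the linkage SAP the population is people "who do not have a prior diagnosis of hypertension", so its similar list had little treatment history to capture. In the severe-hypertension trial everyone enters with raised pressure, so baseline control cannot serve, and treatment at entry is the natural equivalent.

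At stake are some precision in the primary comparison and the ability to answer a reader who sees an arm imbalance in treated patients in the baseline table.

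**Working it through.** **Step 1: the plan's own figure.** The SAP's power appendix assumes 40% control under standard of care, a 20-point increase, about 100 per arm and an unadjusted two-proportion test.

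n per arm = [1.96·√(2·0.5·0.5) + 0.8416·√(0.4·0.6 + 0.6·0.4)]² / 0.20² = (1.3859 + 0.5831)² / 0.04 ≈ 97.

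Power is 81.2% at 100 per arm. The detectable difference is 19.7 points at 100 per arm and 22.0 points at 80 per arm. The stated figures reproduce, and none of them relies on covariate adjustment.

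**Step 2: baseline for the comparison, 98 versus 102.** Here 1/98 + 1/102 = 0.020008.

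- SE under the alternative = √(0.24 × 0.020008) = 0.0693.
- SE under the null, with pooled proportion 0.498, = √(0.498 × 0.502 × 0.020008) = 0.0707.
- Power = Φ[(0.20 − 1.96 × 0.0707) / 0.0693] = 81.2%.

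**Step 3: adding a binary treatment covariate.** Let q be the share treated at entry and d the gap in week-24 control between treated and untreated. The documents give neither, so q = 10-50% and d = 0-30 points are assumptions. The covariate is also assumed independent of the variables already listed.

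- Variance explained: R² = q(1−q)d² / 0.24.
- Both standard errors are multiplied by √(1−R²).
- Equivalent extra participants: 200·R²/(1−R²).
- A 1.96-SD chance imbalance: 1.96·√[q(1−q) × 0.020008]. The shift in an estimate not adjusted for it is this imbalance times d.

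| q | d (points) | R² | SE change | Extra participants | Power | 1.96-SD imbalance (points) | Shift (points) | Shift / SE |
|---|---|---|---|---|---|---|---|---|
| 10% | 0 | 0% | 0% | 0 | 81.2% | 8.3 | 0 | 0 |
| 10% | 30 | 3.4% | −1.7% | 7.0 | 82.5% | 8.3 | 2.5 | 0.36 |
| 30% | 20 | 3.5% | −1.8% | 7.3 | 82.6% | 12.7 | 2.5 | 0.37 |
| 30% | 30 | 7.9% | −4.0% | 17.1 | 84.3% | 12.7 | 3.8 | 0.55 |
| 50% | 20 | 4.2% | −2.1% | 8.7 | 82.8% | 13.9 | 2.8 | 0.40 |
| 50% | 30 | 9.4% | −4.8% | 20.7 | 84.9% | 13.9 | 4.2 | 0.60 |

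Worked example, last row: R² = 0.25 × 0.09 / 0.24 = 0.094; √(1 − 0.094) = 0.952; imbalance = 1.96 × √(0.25 × 0.020008) = 0.139; shift = 0.139 × 0.30 = 0.042.

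**Step 4: validity without the covariate.** In 20,000 simulated null trials at q = 50% and d = 30 points, with 40% control overall, the unadjusted mean estimate was −0.0001 and type I error 5.4%. With the covariate, fitted by linear regression with robust standard errors rather than the SAP's TMLE, type I error was 5.2%. The empirical SE was 0.0693 without the covariate and 0.0661 with it. Leaving it out costs precision, not validity.

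**The case against.** The strongest reply is that this is an optional efficiency gain, and much of that reply stands. A reader might infer more from the omission than the documents support:

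- **That the primary result is biased or its power falls short.** Under randomization, leaving out a prognostic covariate does not bias the estimate, and the SE already carries the variability from chance imbalance (step 4). The power figure assumes no adjustment, so the omission cannot lower it.
- **That precision is certainly lost.** Nothing in the documents says how common prior treatment is, how strongly it predicts control, or in which direction. Overlap with age, sex, grade or country would tend to shrink the gains in the table. No actual imbalance is shown, and one of 1.96 SD or more is about a 1-in-20 event.
- **That the missing-outcome analyses shut these variables out.** The characteristics named for the sensitivity analysis in 2.2 are given as examples, and 2.4 names none, so adding them is permitted but not promised. This matters somewhat more than the primary list. If prior treatment predicts both attendance and blood pressure, omitting it could bias a missing-outcome adjustment, and randomization does not protect against that.
- **That the list was simply carried over from the linkage SAP.** That list has two severity grades and site; this one has three grades and country, so it was at least partly adapted.
- **That retention should also adjust for HIV status.** For retention, the linkage SAP says "For this endpoint, the candidate adjustment variables will be expanded to include baseline HIV status". Another trial's choice does not make its absence here an error.

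Timing is also a fair objection. The SAP is dated June 2023, after enrollment began in May 2022 and with the randomized numbers known, and section 2.7 already describes one data-handling step in the past tense. A change to the primary candidate set could be seen as post hoc.

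**Conclusion.** The point holds as a low-cost improvement, not as an error in the primary analysis. Two baseline variables that are recorded, free to vary and not stratified on are outside a closed candidate list. The procedure cannot use them, although Protocol 15.2 and the sister SAPs give good reason to offer them.

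Over the assumed range the benefit runs from nothing to a 4.8% smaller SE, worth up to about 21 participants on 200, with power of 81.2% to 84.9%. In the mid case (30% treated, 20-point gap) it is 1.8% of the SE and 82.6% power. A 1.96-SD imbalance would shift an unadjusted estimate by 0 to 4.2 points, at most 0.6 of an SE. These sizes rest on assumed prevalence, assumed prognostic strength and independence from the listed covariates. That the variables are missing from the list rests on the documents alone.

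**What to change.** In 2.1, add two candidate adjustment variables: prior hypertension diagnosis (yes/no) and on antihypertensive medication at enrollment (yes/no). Define the second as medication already being taken on arrival at the initial clinic visit, which precedes randomization. Name both in the missing-outcome TMLE in 2.2 and 2.4.

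Record the change, with its date, before anyone sees outcomes by arm. The documents do not say whether that has already happened. If it has, keep the primary analysis as written and report the extended list as a labelled sensitivity analysis.

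The cost is a few lines of SAP text and no new data. The downside is minimal: the procedure chooses the whole combination of variables and estimators with the lowest cross-validated variance, and no adjustment remains a candidate.
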